3.9 Safety Analysis

Safety assessments include AEs, serious adverse events (SAEs), vital sign measurements, clinical laboratory evaluations (hematology, chemistry) and electrocardiograms (ECGs). Unscheduled visits for safety assessments will not be presented in by visit summary tables but will be in listings and shift tables. All safety analyses will be performed using the safety population.

Clinically significant PE findings will be captured as AEs.

3.9.1 Adverse Events

AEs will be coded using the MedDRA dictionary (Version 22.0 or higher). TEAEs are any AEs occurring or worsening in severity after the first administration of study medication. All AEs (including SAEs) will be graded using the 5-point CTCAE V5.0 scale (mild, moderate, severe, life threatening, or death). Causality with study treatment will be classified as: definitely related; probably related; possibly related; unlikely related; not related.

The number (N) and percentage (%) of patients who experienced at least one TEAE will be summarized by dose group, including tabulation by:

- SOC and PTs within each SOC in decreasing total frequency
- PT in decreasing total frequency
- SOC, PTs, and maximum severity
- SOC, PTs, and relationship to study drug

These analyses will be repeated for Grade ≥3 TEAEs, SAE, TEAEs leading to dose modification, and AE leading to study drug discontinuation.

Subject listings will be provided for AEs, SAEs, AEs resulting in study drug discontinuation and deaths. Time to onset and duration of AEs will be included in listings, along with action taken and outcome.

3.9.2 Clinical Laboratory Evaluation

The summary statistics (including number, mean, SD, median, minimum and maximum) of all laboratory variables and changes from baseline will be calculated for each visit or study assessment by treatment group.

For parameters of white blood cell counts, neutrophils (absolute count), lymphocytes (absolute count), monocytes (absolute count), Hb, platelets, ALP, ALT, AST, GGT, total bilirubin, GFR, plots of mean / mean changes from baseline with the corresponding standard error will be displayed.

For shift tables, laboratory results will be classified using the CTCAE V5.0. All graded laboratory parameters will be summarized separately for hematology and biochemistry. Corresponding shift tables to compare baseline to the worst post-baseline grade within the treatment period will be provided.

A by patient by lab tests by visit listing will be generated for lab results with CTC grade >=3.

3.9.3 Vital Signs

Descriptive statistics for vital signs (weight, heart rate, body temperature, systolic and diastolic blood pressure, pulse rate, and respiratory rate) values and the change from baseline will be presented by treatment group for each scheduled assessment time point.

A by patient by visit listing will be generated for vital signs.

3.9.4 ECG

Descriptive statistics for ECG parameters (i.e., heart rate, PR interval, RR interval, QRS interval, QT interval, and QTcF interval) at each time point with triplicate ECGs will be presented for the values and change from baseline scores (QTcF is the QT interval using Fridericia's correction which is calculated by QTcF = QT/RR^{1/3}). In addition the maximum change from baseline will be calculated for each subject and summarized for each treatment group.

The number and percentage of subjects with observed QTcF values that satisfy the following conditions will be presented by treatment group and study visit:

- ≤ 450 millisecond (ms)
- $>450 \text{ to} \le 480 \text{ ms}$
- >480 to ≤ 500 ms
- > 500 ms

The number and percentage of subjects having change from baseline QTcF values that satisfy the following conditions will be presented by treatment group and study visit:

- ≤ 0 ms
- >0 to ≤ 30 ms
- >30 to ≤ 60 ms
- > 60 ms

A by patient by visit listing will be generated for ECG results.

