PE Physical examination
PFT Pulmonary function test

PK Pharmacokinetic
QD Once daily

QOD Once every other day

QTc(F) Corrected QT interval using Fridericia's formula

ROCK Rho-associated protein kinase

SAE Serious adverse event SAP Statistical Analysis Plan

SHAQ-DI Scleroderma Health Assessment Questionnaire—Disability Index

SOC System organ class
SSc Systemic sclerosis

SUSAR Suspected unexpected serious adverse reaction

TEAE Treatment-emergent adverse event TGF-β Transforming growth factor-beta

TLC Total lung capacity
Treg Regulatory T-cells
ULN Upper limit of normal
VAS Visual Analog Scale

27 May 2021

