3.5 EXCLUSION CRITERIA

- 1. Subject has corrected QT interval using Fredericia's formula (QTcF) > 450 ms
- 2. Ongoing use or current use of concomitant medication known to have the potential for QTc prolongation;
- 3. Female subject who is pregnant or breastfeeding
- 4. Participated in another study with an investigational drug within 28 days of study entry (for studies involving biologics, within 3 half-lives of the biologic)
- 5. History or other evidence of severe illness or any other conditions that would make the subject, in the opinion of the Investigator, unsuitable for the study
- 6. Chronic heart failure with New York Heart Association Classes II, III, and IV
- 7. Acute or chronic liver disease (e.g., cirrhosis)
- 8. Positive human immunodeficiency virus (HIV) test
- 9. Active hepatitis C virus (HCV), hepatitis B virus (HBV), or positive whole blood tuberculin test
- 10. Diagnosed with any malignancy within 3 years of enrollment, with the exception of basal cell or completely resected squamous cell carcinoma of the skin, resected in situ cervical malignancy, resected breast ductal carcinoma in situ, or low-risk prostate cancer after curative resection
- 11. Has had previous exposure to belumosudil or known allergy/sensitivity to belumosudil or any other ROCK2 inhibitor
- 12. Scleroderma renal crisis within 4 months prior to enrollment
- 13. FVC < 50% Predicted

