6.2 SAFETY

6.2.1 Safety Endpoints

Also see Section 9 for additional detail on AEs.

AEs and SAEs

- Hematological and clinical chemistry parameters
- Vital signs: change from baseline in systolic blood pressure, diastolic blood pressure and heart rate
- 12-lead ECG: mean and maximum change from baseline in QTcF

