6.2.2 Vital Signs

Seated pulse rate and blood pressure measurements will be performed as outlined in the Schedule of Assessments (Appendix A). Measurements will be taken with the subject sitting, having rested in this position for at least 5 minutes. Vital signs should be taken before ECGs and other scheduled assessments.

6.2.3 12-Lead ECG

Twelve-lead ECGs will be performed as outlined in the Schedule of Assessments (Appendix A). ECGs will be recorded after the subject has rested in the supine position for at least 5 minutes and should be performed prior to any blood sample collections.

The following ECG parameters will be collected: PR interval, QRS interval, and QTc or QTcF. The ECG findings will be evaluated by a qualified physician for the presence of abnormalities (qualitative assessment). The physician will assess each ECG as normal, abnormal/not clinically significant, or abnormal/clinically significant.

Abnormalities in the ECG that lead to a change in subject management or result in clinical signs and symptoms are considered clinically significant for the purposes of this study and will be recorded in the AE eCRF. If ECG abnormalities meet criteria defining them as serious, they must be reported as an SAE (Section Error! Reference source not found.).

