9.6.2 Stopping Criteria for Subjects

Subjects will be discontinued from the study at any time for the following reasons:

- 1. Grade \geq 3 LFT increase (AST, ALT, or total bilirubin)
- 2. Grade \geq 3 clinically significant toxicity considered related to belumosudil

3. QTc > 500 ms or AE of *Torsade de Pointe*

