9.9 SAFETY ANALYSES

Treatment exposure will be summarized.

The TEAEs will be evaluated using the CTCAE v5.0. The total sample size of 20 subjects per belumosudil dose group will provide > 90% probability of one or more belumosudil subjects experiencing an AE that has an underlying rate of \geq 14% and > 80% probability of one or more subjects in the study experiencing an AE that has an underlying rate of \geq 10%.

The TEAEs will be summarized overall and by group using Medical Dictionary of Regulatory Activities Version 21.0 (MedDRA v21.0) or higher, System Organ Class (SOC) and preferred term (PT), classified from verbatim terms. The incidence and percentage of subjects with at least one occurrence of a preferred term will be included, according to the most severe grade using a 5-point scale (mild, moderate, severe, life threatening, or death). The number of events per preferred term will also be summarized. Causality (relationship to study treatment) will be summarized separately.

AEs, SAEs, related AEs, related SAEs, Grade ≥ 3 AEs, related Grade ≥ 3 AEs, and AEs leading to withdrawal or treatment discontinuation will be summarized overall and by group according to SOC and PT. Adverse events will also be presented in listings. Duration of AEs will be determined and included in listings, along with action taken and outcome.

Laboratory results will be graded; Incidence of laboratory abnormalities will be summarized. The worst on-study grade after the first dose of study drug will be summarized. The incidence of Grade ≥ 3 laboratory abnormalities under treatment and shifts in toxicity grading from baseline to highest-grade post-baseline will be displayed.

Vital sign measurements and ECGs will be summarized by group at each scheduled time point using descriptive statistics and included in data listings.

Page 70 of 99

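### Read literally, SAP 3.9.4 ties descriptive ECG statistics, including mean QTcF change, to triplicate ECGs that the protocol requires at none of its 17 scheduled ECGs

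*SAP*

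**What the plan says.** SAP 3.9.4 names six ECG parameters (heart rate, PR, RR, QRS, QT and QTcF). It gives descriptive statistics for their values and changes from baseline, running to "QT interval, and QTcF interval) at each time point with triplicate ECGs". It then adds three outputs without that condition:

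- a maximum change: "In addition the maximum change from baseline will be calculated for each subject and summarized for each treatment group";
- counts of subjects in four bands of observed QTcF, and in four bands of QTcF change, by treatment group and study visit;
- an ECG listing by patient and visit.

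The protocol sets a wider scope. The synopsis and Section 9.9 both state: "Vital sign measurements and ECGs will be summarized by group at each scheduled time point". Section 6.2.1 lists as a safety endpoint: "12-lead ECG: mean and maximum change from baseline in QTcF".

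On how ECGs are taken, Protocol 6.2.3 refers to Appendix A and requires supine rest of at least five minutes and recording before blood sampling. It gives no number of replicates. SAP 2.3 refers to the same Appendix A for the schedule.

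**The concern.** The qualifier on triplicates reads as a condition for a time point to enter the table. If no visit is required to have triplicates, a programmer who follows the sentence has no visit that is certain to qualify. The table would then fall short of what Protocol 9.9 promises.

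At stake is the by-visit mean change in QTcF, which is one half of a named safety endpoint. The other half, the maximum change, has its own unconditional sentence. The band tables give counts and the maximum gives one value per subject, so neither yields a mean change at a visit. The trial treats QT as a risk to manage: it has an entry limit on QTcF, a ban on QT-prolonging drugs and a QTc stopping criterion. The placebo-controlled period is where a mean change is most informative.

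**Working it through.** The plan states no figure for this point, so the check is a count and a comparison of texts.

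**1. Scheduled ECGs (12-lead ECG row of Protocol Appendix A).**

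| Column | Marks |
|---|---|
| Screening | 1 |
| Baseline | 1 |
| Day 15 | 1 |
| Weeks 4 to 52, every 4 weeks | 13 |
| 28-day follow-up | 1 |
| Unscheduled | 1 |
| Total | 18 |

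Scheduled: 18 − 1 = 17. The visit lists in Protocol 5.1 to 5.6 agree.

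**2. Post-baseline ECGs, where a change can be computed.** 17 − 2 (screening and baseline) = 15. By period:

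- double-blind (Day 15 and Weeks 4, 8, 12, 16, 20, 24, 28): 8
- open-label (Weeks 32, 36, 40, 44, 48, 52): 6
- follow-up: 1
- sum: 8 + 6 + 1 = 15

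**3. Visits with a triplicate requirement.** Protocol 6.2.3, the Section 5 visit lists, Appendix A and its footnotes contain none. The word triplicate occurs only in SAP 3.9.4. The SAP takes its schedule from Appendix A, so it adds no triplicate schedule of its own. Result: 0 of 17.

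**4. Time points sure to appear in the mean-change table.**

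| Wording followed | Post-baseline time points assured |
|---|---|
| SAP 3.9.4, literally | 0 of 15 |
| Protocol 9.9 and synopsis | 15 of 15 |

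**5. Which ECG outputs carry the condition.**

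| Output in SAP 3.9.4 | Triplicate condition? |
|---|---|
| Descriptive values and changes from baseline | Yes |
| Maximum change per subject | No |
| QTcF value bands by visit | No |
| QTcF change bands by visit | No |
| Listing by patient and visit | No |

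**6. Neighbouring SAP sections.** Laboratory statistics (3.9.2) are given for each visit, and vital signs (3.9.3) for each scheduled assessment. Only the ECG section has a qualifier of this kind.

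**7. If triplicates are in fact recorded.** The SAP gives no rule for averaging them. Its general baseline (3.1.6) is the last non-missing value before first dose, which could select a single replicate.

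**The case against.** The strongest reply is that the phrase is a mistaken description of how ECGs are taken, perhaps template text, and was never meant to drop single-ECG visits. The surroundings support this. SAP 3.9 keeps unscheduled visits out of by-visit safety tables, which presupposes such tables for scheduled visits. SAP 3.9.4 itself tabulates QTcF bands by visit without the condition, and the SAP says it implements the protocol. That reading is plausible and may be what was intended. It does not remove the point, because nothing in the documents says so and the sentence as written conflicts with Protocol 9.9.

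A second reply also stands: 0 of 15 counts what the wording assures, not data lost. The protocol is silent on replicates and does not forbid them, and the eCRF is not among the documents. Mean change could be computed from single ECGs already planned.

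A reader might infer more in two directions.

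- **That QTcF safety will go unreported.** The documents do not support this. Four of the five outputs tabulated in the working are unrestricted, and neither subject monitoring nor any stopping decision depends on the phrase.
- **That QTcF cannot be derived, or that the stopping rule is ambiguous.** Protocol 6.2.3 says "The following ECG parameters will be collected: PR interval, QRS interval, and QTc or QTcF", so QT, RR and ECG heart rate are not listed, and Section 9.6.2 writes "QTc > 500 ms or AE of". But the eCRF may hold those fields, a QTcF recorded directly needs no derivation, and exclusion criterion 1 already requires sites to obtain QTcF. Fridericia is the only correction named: the abbreviation list has "QTc(F) Corrected QT interval using Fridericia's formula". The unqualified QTc is most likely shorthand, so neither item is shown to be a defect.

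**Conclusion.** The point holds as a wording conflict between SAP and protocol. Read literally, SAP 3.9.4 assures a mean QTcF change at none of 15 post-baseline scheduled ECGs, eight of them in the double-blind period, where the protocol promises all 15. The affected outputs are the descriptive ECG values and changes, and through them the mean-change half of the QTcF endpoint in Protocol 6.2.1. Efficacy, including CRISS, is untouched.

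This rests on two assumptions: that the qualifier is applied as a condition, and that no instruction outside these documents orders triplicates. If either fails, the practical loss shrinks. The phrase would still need correcting in the first case, and an averaging rule would be missing in the second. It is a low-priority correction, worth making because it costs little and secures the table for a named safety endpoint.

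**What to change.** In SAP 3.9.4 only, replace the phrase that limits the table to triplicate time points with: *at each scheduled time point (using the mean if replicates were recorded)*. This matches Protocol 9.9 and the synopsis, and it supplies the missing averaging rule should any site record replicates. If replicates exist before first dose, apply the same mean to the ECG baseline.

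The cost is one phrase in the SAP, with no new ECGs and no new data fields. Leave the parameter list in Protocol 6.2.3 and the QTc label in 9.6.2 as they are. Changing them would mean a protocol modification with ethics submission under Protocol Section 12, for no clear gain.

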3.10 Pharmacokinetic Analysis

Further details will be described in the Pharmacokinetic Analysis Plan.

3.11 Pharmacodynamics Analysis

Further details will be described in the Pharmacodynamics Analysis Plan.

3.12 Exploratory Objectives Analysis

The exploratory objectives are listed as below and will be described in the Exploratory Analysis Plan.

- To evaluate changes in biomarkers of endothelial cell dysfunction, fibrosis, immune system function, and cytokine alterations from subjects receiving belumosudil or placebo
- To assess histology and gene expression from skin biopsies taken from subjects at baseline, Week 24 and optionally at Week 52

